3	5	8	40	72.00	60.00

Note – the first 6 evaluable patients enrolled will be treated at Dose Level 1 Please refer to section 10.0

Version 09/11/2025 page 10 of 63

SCHEDULE OF ACTIVITIES

	Screening	Pre- treatment ⁸	Radiation	1-2 Weeks post RT	6-8 Weeks post RT	3 Mo post RT ¹	6 Mo post RT ¹	9 Mo post RT ¹	12 Mo post RT ¹	
Informed consent	X^2									
H&P / PS / weight / DRE ¹³	X^2		X^3	X	X	X	X	X	X	
MRI pelvis ⁴	X^2				X	5	X	X	X	
CT chest / abdomen / pelvis with contrast ⁶	X^2				X ⁶		X	X	X	
Endoscopy ⁷	X^2				X	15				
OPTIONAL biopsy	$X^{2, 15}$				Х	ζ				
CBC w/diff	X^2	X^2			X^9		X			
CMP	X^2	\mathbf{X}^2			X^9		X			
CEA		X			X^9		X			
SCCA		X			X ⁹		X			
CRP		X			X ⁹		X			
LDH		X			X ⁹		X			
Pregnancy test	$X^{10,11}$									
Radiation therapy			X^{12}							
EORTC QLQ-C30		X		X		X	X	X	X	
EORTC QLQ-C29		X		X		X	X	X	X	
Adverse events		X	X^3	X	X	X	X	X	X	

- 1. +/- 2 weeks
- 2. No more than 60 days prior to registration. Screening and baseline labs can be the same draw provided the timing aligns.
- 3. Performed once during radiation therapy.
- 4. Cross-sectional imaging with either MRI or CT is acceptable.
- 5. MRI pelvis and CT chest/abdomen with contrast may be obtained 6 weeks to 3 months after radiation completion with a RECIST read at 3 months only.
- 6. If PET/CT scan is done, then CT chest/abdomen/pelvis not required.
- 7. Endoscopy with colonoscopy, sigmoidoscopy, or proctoscopy will be performed if feasible after screening.
- 8. Baseline labs and QOL assessments should be performed within 30 days of radiation therapy.
- 9. Labs should be drawn once 6 weeks to 3 months after radiation completion but should be drawn before surgery if the patient undergoes salvage surgery.
- 10. Mandatory for women of childbearing potential.
- 11. Within 14 days of registration.
- 12. 5 fractions over 1 week.
- 13. DRE only to be done if feasible.15. OPTIONAL endoscopy with biopsy performed 6 weeks to 3 months after completion of RT; for research purposes only.
- 15. OPTIONAL screening biopsy to be performed at time of baseline SOC endoscopy.

Version 09/11/2025 page 11 of 63

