10.1.2 TITE-CRM design

The starting dose can have a large impact on the properties of the design. After the trial is completed, most information about the MTD will be obtained if many patients are treated at or near the MTD. Thus, the sooner the choice of dose can converge on the MTD the more effective the trial will be. However, due to the uncertainty of the MTD in the reirradiation of locoregionally recurrent rectal cancer, we will start at the two dose levels lower than the expected MTD to prioritize safety. Therefore, our starting dose for this trial will be PTV total dose of 30 Gy.

The next thing to be considered is the dose escalation rules. For this trial, we will only allow a single dose level escalation per new patient enrolled on the trial.

Version 09/11/2025 page 40 of 63

Therefore, if the previous patient was treated at dose level, d_k , then a new patient can only be treated at dose levels d_{k+1} or lower. In order to determine at which level to treat the new patient, we will use a weighted, cumulative time of exposure approach.

The total length of follow-up for DLT for any patient is 6 months from the start of radiation therapy. In order to efficiently and effectively determine the MTD, we allow for a dose change when the cumulative time of exposure is 6 months. Additionally, since previously published data shows that most toxic events occur within the first 6 months from start of treatment, we also implement a linear weighting function wherein the first 6 months accounts for 75% of the follow-up where the last 3 months attributes 25% of the follow-up information. The dose for the next patient is selected so that the estimated probability at that dose is close to the target level.

A feature of the dose escalation part of the TITE-CRM program is the flexibility in specifying the margin for the dose selection. This allows the selection of the dose level for the next patient that may have an estimated probability of toxicity larger than the target level but less than the target level plus the margin. It finds the dose closest to the target probability even if it has a higher estimated probability. For this trial we set the admissible margin to be 5%, therefore, the MTD will be chosen as the dose that yields a posterior toxicity estimate closest to 35% while being between 30% and 40%. The admissible margin is also used to help determine stopping rules for the trial.

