In order to account for the possibility of poor initial outcomes we will employ a run-in of 6 patients, meaning that the minimum number of treated patients will be 6. If after these 6 patients, or any other time during the trial, the lowest dose level has a posterior probability higher than 40% then the trial will stop.

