10.2 Simulation and Sample Size Calculations

The TITE-CRM manual details methods for utilizing trial simulation in order to obtain estimated posterior probabilities on toxicity estimates. We utilized the simulation program to determine the efficacy of our trial and obtain estimates for needed sample size. While there is no exact power calculation for this type of trial, the effectiveness of the trial's sample size can be determined by looking at the stability of the posterior probability under different prior probabilities.

We ran 1000 simulations under various increasing and decreasing prior probability estimates utilizing the previously described rules and assumptions for this trial and saw sufficient stability in posterior probability estimates with a sample size of 20 patients with a run-in of 6 patients. Simulations showed that approximately 95% of the time the trial will come to completion and the MTD will fall between the 3rd and 5th dose level 89% of the time. Therefore, we will use a fixed sample size of 20 patients for this trial. The posterior probability distribution of these 1000 simulations follow in the next table.

Version 09/11/2025 page 41 of 63

Dose Level	Estimated	Mean
	initial	Posterior
	toxicity	toxicity (SD)
d-1	0.25	0.328 (0.434)
1	0.30	0.38 (0.453)
(Starting		
Dose)		
2	0.35	0.43 (0.463)
3	0.40	0.479 (0.464)

Summary of simulation with estimated posterior probabilities. SD, Standard Deviation

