
10.2.2 Recommended Phase 2 Dose

The MTD will be estimated using the proposed TITE-CRM model. After the phase I study, the MTD will be chosen as the dose that yields a posterior toxicity estimate closest to 35% while being between 30% and 40%.

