10.2.5 Analysis Plan

The primary endpoint of the study is to determine the maximum tolerated dose (MTD) of reirradiation using hypofractionated IMPT for patients with locoregionally recurrent rectal cancer. The MTD will be defined as the dose associated with a 35% probability of dose-limiting toxicity (DLT) as described above.

The secondary endpoints are clinical complete response rate, freedom from locoregional progression (FFLP), overall survival (OS), progression-free survival (PFS), PRO QOL, and adverse events as defined by CTCAE version 5.

Descriptive statistics will be calculated on all variables. Frequencies will be computed for all binary/categorical variables, and continuous variables will be summarized using medians, quartiles, and ranges. Next all variables will be compared with the historical data using Chi-square tests for binary/categorical variables and t-tests for continuous variables.

All the survival events will be measured from the end of radiation therapy and subjects who do not develop events will be censored at the last follow-up. Patients with distant metastasis will be continued to be followed for locoregional tumor recurrence until the last follow-up or time of death whether. Death will be analyzed as a competing cause in FFLP. Kaplan-Meier curves will be performed to compare the freedom from locoregional progression (FFLP), progression-free survival (PFS) and overall survival (OS). Cox proportional hazard model with log-rank test will be used to explain the correlation between explanatory variables and survival times.

Version 09/11/2025 page 43 of 63

Adjusted hazard ratios (HR) and the corresponding 95% confidence intervals (CI) will be reported.

PRO QOL questionnaires (Appendix B and C) will be tabulated for each domain and summed to generate a composite global QOL score. Repeated measures ANOVA will be used to compare QOL scores collected at baseline and at 1-2 weeks, 3 months, 6 months, 9 months, and 12 months after RT.

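### Section 10.2.2 can name as MTD and recommended phase 2 dose a level that no patient received

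*Combined protocol and SAP*

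**What the plan says.** The final choice rests on the model alone. Section 10.2.2 states "The MTD will be estimated using the proposed TITE-CRM model" and then gives its single criterion: "the MTD will be chosen as the dose that yields a posterior toxicity estimate closest to 35% while being between 30% and 40" per cent. Section 10.1.2 has the same criterion, and the band comes from there: "For this trial we set the admissible margin to be 5" percentage points. Section 10.2.5 adds "The MTD will be defined as the dose associated with a 35% probability of dose-limiting toxicity (DLT) as described above".

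Four other provisions might be expected to tie the choice to treated levels. None does.

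- **Step limit (10.1.2):** "we will only allow a single dose level escalation per new patient enrolled on the trial". Section 10.2.1 applies it to the next patient's assignment, not to the final selection.
- **Run-in (after 10.1.2):** "we will employ a run-in of 6 patients, meaning that the minimum number of treated patients will be 6". This is a minimum for the whole trial. The Schema note says "the first 6 evaluable patients enrolled will be treated at Dose Level 1".
- **Replacement (10.2.3):** refills a level only after a withdrawal for reasons other than toxicity.
- **Evaluability (5.4):** defines who counts for the MTD endpoint but sets no number per level.

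The sample size is set in 10.2: "Therefore, we will use a fixed sample size of 20 patients for this trial". Section 10.1.2 expects the trial to learn most when many patients are treated close to the MTD, but does not make that a condition of naming it.

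**The concern.** Assignment is protected by the step limit; the final choice is not. Once the last patient has been observed, the model is refitted to all 20 outcomes and the nearest level is named. Some of those outcomes arrive after the last dose has been assigned, so no later assignment can respond to them. The initial estimates in the 10.2 table are only 5 points apart, so one or two DLTs can move the choice to a neighbouring level. If nobody was treated there, its toxicity is known only through the assumed curve.

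At stake is the label. Section 2 makes tolerability the basis for deciding on further trials. A level carried forward as the MTD would normally be read as one at which toxicity was observed and found acceptable.

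**Working it through.** **Inputs from the documents.** Target 35%, band 30-40% (10.1.2, 10.2.2). Initial estimates 0.25 / 0.30 / 0.35 / 0.40 for Levels -1 / 1 / 2 / 3 (10.2 table). 20 patients; DLT window 6 months; start at Level 1; one-level steps; stop if the posterior at the lowest level exceeds 40%. Recruitment 36 months (Protocol Summary).

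**Inputs assumed, because the plan does not state them.** One-parameter power model, DLT probability at level i = (initial estimate)^x, with x = exp(a) and a normal with mean 0; prior SD 0.5 to 1.34; constant accrual; several true DLT curves. Section 10.1.1 also mentions five levels with estimates from 0.05 to 0.25, and 10.1.2 describes weights that run to 9 months. The four-level table and linear 6-month weights are used here.

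**The plan's own figures.** Section 10.2 reports about 95% of trials completing and 89% with the MTD between the 3rd and 5th level. These cannot be reproduced without the model, prior variance, true curve and accrual rate, and the dose table has no 5th level. They also do not say how often the named level was untried.

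**Step 1: late outcomes.** 20/36 = 0.56 patients per month. Over a 6-month window, 0.56 x 6 = 3.3, so about three patients are typically still under observation when the last dose is assigned.

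**Step 2: does the rule permit it?** Take 20 patients, all at Level 1, as an illustration and not a typical path. Ignoring the prior, x solves 0.30^x = DLTs/20.

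- 5 DLTs: x = ln 0.25 / ln 0.30 = 1.151. Level 3 is 0.40^1.151 = 0.348, so Level 3 is named.
- 6 DLTs: x = 1. Level 2 is 0.35, so Level 2 is named.
- 8 DLTs: x = ln 0.40 / ln 0.30 = 0.761. Level -1 is 0.25^0.761 = 0.348, so Level -1 is named.

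With prior SD 1.16 and posterior means the choices are the same: 0.360 at Level 3, 0.360 at Level 2 and 0.355 at Level -1. No patient received any of the three named levels.

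**Step 3: do paths that follow the allocation rules reach it?** Three simulated trials (prior SD 1.16), with patients and posteriors at Levels -1/1/2/3:

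| Patients | DLTs | Posteriors | Named | Treated level in 30-40%? |
|---|---|---|---|---|
| 4/16/0/0 | 6 | 0.267/0.318/0.368/0.418 | Level 2, untried | Yes, Level 1 |
| 2/11/7/0 | 5 | 0.200/0.247/0.295/0.345 | Level 3, untried | No |
| 0/9/4/7 | 9 | 0.358/0.410/0.459/0.507 | Level -1, untried | No |

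**Step 4: how often?** Runs of 3000 trials per cell, first six patients at Level 1. Because steps up are one level at a time from Level 1, the treated levels have no gaps. An untried level is therefore either above or below all of them, and the two shares add.

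| True curve | Prior SD 0.5: above + below | Prior SD 1.16: above + below |
|---|---|---|
| Plan's 0.25-0.40 | 4.1 + 1.4 = 5.5% | 1.9 + 2.3 = 4.2% |
| Lower | 0.6 + 0.3 = 0.9% | 0.7 + 0.7 = 1.4% |
| Steeper | 2.4 + 1.8 = 4.2% | 0.7 + 3.5 = 4.2% |
| Higher | 2.1 + 5.8 = 7.9% | 0.9 + 8.8 = 9.7% |

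These are shares of trials that declare an MTD. Under the plan's curve 76.7% (SD 0.5) and 43.3% (SD 1.16) of trials did so. As a share of all trials that is 0.767 x 5.5% = 4.2% and 0.433 x 4.2% = 1.8%.

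Separately coded power-model runs, with prior SD 0.5 or 1.34 and five curves, extend the range to 0-12% of declared MTDs, 0-5% of all trials and 0-5% above every treated level. The range under the plan's curve is about 2-7%. Adding a logistic model and the 9-month weights raises the upper end to 16% of declared MTDs.

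**Not modelled.** Section 10.1.2 also requires 6 months of cumulative exposure before a dose change. One reading of it was tried, for escalation only, and the untried share did not fall consistently.

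**The case against.** The best reply is that this is how the CRM works. It estimates every level through one curve, the plan openly adopts that method, and allocation aims at the same 35%, so most patients will be near the chosen level. An untried choice is uncommon and often lies below all treated levels, where the data come from higher doses. All of that stands. It limits the size of the problem, but does not supply the missing condition.

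A reader might also infer three stronger points that the documents do not support.

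- **That thinly treated levels are the main defect.** A level with fewer than three patients is named in 3-22% of declared MTDs in one set of runs, and two patients without a DLT give an exact 95% interval of 0-84%. But the plan sets no minimum number, any such number is debatable, and the share is sensitive to the exposure rule. With that rule in one reading, the share with one or two patients under the plan's curve fell from 9-15% to 6-7%.
- **That nobody could see the level was untried.** Section 10.2.1 has the program list patients and DLTs by dose and calculate 95% credible intervals, and Appendix F lists dose level and DLT for each patient. What is missing is the instruction to put these figures beside the final MTD.
- **That patients in this trial could jump to an untested dose.** The step limit governs assignment and is not in question here.

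**Conclusion.** The point holds as a gap in the selection rule. Under 10.2.2 as written, an untried level can be named as MTD and recommended phase 2 dose, and no other section prevents it. That much follows from the text.

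The frequency is modest: about 0-12% of declared MTDs, roughly 2-7% under the plan's own curve, and about 0-5% of all trials. The more worrying direction, above every treated level, accounts for about 0-5% of declared MTDs. These ranges assume the power model, prior SD 0.5 to 1.34, linear 6-month weights and accrual over 36 months. The plan's actual model and prior could move them. This is not an error in TITE-CRM.

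**What to change.** In 10.2.2:

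1. Define the MTD as the level with posterior closest to 35%, within 30-40%, among levels at which at least one patient was treated and completed DLT observation. Completed means a DLT occurred or the full 6-month window passed without one. Section 10.1.1 ends observation at a DLT, so a patient with an early DLT must count.
2. If no treated level lies in the band, report the model's choice and its posterior as an extrapolation, not as the MTD.
3. Report beside the MTD the number treated, the number of DLTs and the 95% credible interval at that level. This makes a thin level visible without a minimum number.

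The cost is a few sentences, with no extra patients and no change to dose assignment. In a small share of trials the named level becomes a treated neighbour (as in the first trial of Step 3), or no MTD is declared (as in the other two). If the untried choice lies below all treated levels, the treated neighbour is the higher of the two, though still inside the band. The posteriors that the program gives for each level should then be shown together.

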10.2.3 Replacement of Subjects that are not Evaluable

Patients who withdraw from the dose escalation component of the trial for any other reason than toxicity and who have not already developed a dose-limiting toxicity (DLT) at that point will be replaced by recruiting another patient at the same dose level.

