5.4 Definitions of Evaluability

Endpoint	In order to be evaluable for this endpoint, a		
	patient must		
	Have received at least one fraction of study		
	radiation. Patients will be evaluated for DLTs		
Maximum tolerated dose	from the start of treatment through 6 months		
	after the start of treatment. DLT is defined in		
	Section 5.2.1.		
Clinical complete response rate.	Have received at least one fraction of study		
	radiation and undergone response assessment by		
	DRE, endoscopy, and/or cross-sectional		
	imaging.		
Freedom from locoregional	Have received at least one fraction of study		
progression (FFLP) at 12 months.	radiation and undergone response assessment.		
Overall survival at 12 months.	Have received at least one fraction of study		
	radiation		
Progression-free survival at 12	Have received at least one fraction of study		
months.	radiation and undergone response assessment.		

Version 09/11/2025 page 27 of 63

Patient reported quality of life.	Have completed the EORTC QLQ-C30 and/or QLQ-CR29 QOLs at pre-treatment and a minimum of one post-treatment time point
Toxicity	Have received at least one fraction of study radiation. Patients are evaluated from first receiving study radiation until 12 months after the conclusion of radiation.
Association of pre-treatment SCCA and post-treatment SCCA with PFS and OS at 6 months.	Have had blood drawn for SCCA at screening and after completion of study radiation
Levels of serum inflammatory markers.	Have had blood drawn for CRP and LDH after completion of study radiation

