10.2.1 Workflow

The first patient will be enrolled on the trial and treated at PTV total dose 30 Gy, which is one dose level below the hypothesized MTD. That patient will be entered into the titecrm.sas program and follow-up will begin from start of treatment.

For the purposes of this trial, the patient will be followed from start of treatment until the patient completes 12months of follow-up, has a DLT, or is lost to follow-up. If any of these endpoints occur, the statistician will be notified and the date corresponding to the event will be entered into the program. While there is a maximum follow-up of 6 months for observation of possible toxicities, sometimes patients have a delay in their treatment resulting in the need for a prolonged observation period. This delay will be accounted for, as needed, for this study to ensure a complete 6-month follow-up.

When a new patient is enrolled on the trial, the statistician will be notified of the date of enrollment. At that time the statistician will update the follow-up for all patients currently on the trial and determine the dose that will be administered for the new patient. We will utilize the cumulative time of exposure method, which will allow the contribution of patients with no DLT at this time to be partially weighted consistent with their time observed. We will also utilize the weight function to place more emphasis on the first 6 months follow-up (75% weight) compared to the last 3 months of follow-up (25% weight). At this point, the program provides a summary of the number of patients treated at each dose so far, along with the number of DLTs that have occurred. The posterior probability and 95% credible intervals of dose limiting toxicity for each dose level is calculated. At this point, the model determines the dose level that has an estimated toxicity rate closest to 35% within the 5% admissible margin.

The newly enrolled patient will be enrolled in the corresponding dose level if that dose level is within one dose level from the dose level the most current patient is enrolled on. If the suggested dose level is more than one dose level from the current dose level the next patient will be enrolled on the dose level that is closest to the current level in the direction of the dose level determined from the estimated

Version 09/11/2025 page 42 of 63

posterior probability. This continues until the trial has accrued all 20 patients or, if after 6 patients are enrolled, the estimated posterior.

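### Section 10.2.3 doses a replacement patient at the withdrawn patient's old level, which can override the model-set dose, the 40% ceiling and the one-level limit

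*Combined protocol and SAP*

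**What the plan says.** Three sections of the combined protocol and SAP set a patient's dose.

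- **10.2.3** covers patients who leave the dose-escalation part for a reason other than toxicity and have had no DLT by then. Each "will be replaced by recruiting another patient at the same dose level".
- **10.2.1** has the statistician, at each new enrolment, update everyone's follow-up and "determine the dose that will be administered for the new patient". The rule is that "the model determines the dose level that has an estimated toxicity rate closest to 35% within the 5% admissible margin", and the assigned level must lie within one level of the most recent patient's.
- **10.1.2** lets the next dose have an estimated DLT probability "larger than the target level but less than the target level plus the margin". With a 35% target and a 5% margin, that is a 40% ceiling. It also states that "we will only allow a single dose level escalation per new patient enrolled on the trial".

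Two other places bear on the point. The note under the Schema says that "the first 6 evaluable patients enrolled will be treated at Dose Level 1". Section 5.4 makes a patient evaluable for the MTD on a minimal condition: "Have received at least one fraction of study" radiation.

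No section exempts replacements from 10.1.2 or 10.2.1, and 10.2.3 is not made subject to them. Appendix F only records whether a patient was replaced.

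**The concern.** A replacement is a newly enrolled patient, so 10.2.1 and 10.2.3 both claim to set that patient's dose. Refilling the same level suits a cohort design in which each level needs a fixed number of evaluable patients. After the run-in, TITE-CRM has no such cohort. Section 1.7.2 states the opposite principle, that later patients are treated at the current target dose.

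The follow-up window is 6 months, so the model may have moved well away from a level between one patient's entry and that patient's withdrawal. Read literally, 10.2.3 then returns a new patient to a dose the accumulated DLTs argue against. These patients have had prior pelvic radiation, section 1.7.3 concedes that organ tolerances are not known for these schedules, and the DLT list includes fistula, perforation, haemorrhage and death.

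**Working it through.** **What can be reproduced.** No figure in the plan is in dispute. The simulation behind the sample size of 20 (section 10.2) cannot be rerun, because the true toxicity curves, model form, prior variance and accrual process are not given. The check is whether the rules can collide in a history the design permits, and how often under stated assumptions.

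**Inputs from the plan.** Prior DLT rates 0.25/0.30/0.35/0.40 for Levels −1/1/2/3 (section 10.2 table); target 0.35; ceiling 0.35 + 0.05 = 0.40; run-in of 6 at Level 1; one-level moves; stop if the lowest level exceeds 0.40 (end of section 10.1); DLT window 6 months; 20 patients in 36 months, so one every 36/20 = 1.8 months.

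**Assumed.** Power model with prior SD 1.16 or 0.5. Two weight shapes: linear over 6 months, or 75% over months 0–3 and 25% over months 3–6. The plan's split into a first 6 and a last 3 months does not fit a 6-month window. Withdrawn patients keep the weight they have earned.

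**Model.** For level *j* with prior rate *s_j*, DLT probability is *s_j*^exp(β), with β ~ N(0, SD²). A DLT contributes *p*; a patient without one contributes 1 − *w·p*, where *w* is the follow-up weight. The estimate is the posterior mean of *p*.

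**Worked history.**

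| Patient | Level | Outcome |
|---|---|---|
| 1–6 | 1 (30 Gy) | 1 DLT |
| 7 | 2 (35 Gy) | no DLT |
| 8 | 3 (40 Gy) | withdraws DLT-free at 5.5 months |
| 9, 10 | 3 (40 Gy) | DLT each |
| 11 | 2 (35 Gy) | DLT |

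The model itself, under the one-level limit, sends patients 7 to 11 along this path. Patient 8 enters at 7 × 1.8 = 12.6 months and leaves at 18.1. The replacement enters at 11 × 1.8 = 19.8 months. By then every other DLT-free patient has full weight (patient 7: 19.8 − 10.8 = 9.0 months). Patient 8's linear weight is 5.5/6 = 0.917.

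| Prior SD (linear weight) | Level −1 | Level 1 | Level 2 | Level 3 | Model's choice |
|---|---|---|---|---|---|
| 1.16 | 0.295 | 0.343 | 0.390 | 0.436 | Level 1 (0.007 from target; Level 2 is 0.040) |
| 0.5 | 0.277 | 0.325 | 0.373 | 0.421 | Level 2 (0.023 from target; Level 1 is 0.025) |

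The other weight shape changes these by at most 0.003. The lowest level is below 0.40, so the trial continues. The model gives 30 or 35 Gy (BED 48 or 59.5 Gy₁₀). Section 10.2.3 gives 40 Gy (72 Gy₁₀), above the ceiling.

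**A history that also breaks the one-level limit** (power model, SD 1.0). Six patients at Level 1 and one at Level 2 have no DLT, and one at Level 3 withdraws early (weight 0.2). Then come four DLTs at Level 3, one at Level 2 and one at Level 1. Estimates are 0.359/0.408/0.455/0.501. The model sets Level −1 and the trial stays open. Section 10.2.3 sends the replacement to Level 3, two levels above the most recent patient, at an estimated 50%. Six model and SD settings all give 48–52% there.

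**How often.** Simulations of 1,000 trials per setting used four assumed curves for Levels −1/1/2/3 (25/30/35/40, 10/20/35/55, 30/40/50/60 and 5/10/20/30%), both SDs and both weight shapes. The table gives the share of trials with at least one such replacement; a dash means not reported.

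| Replacement dose | 5% withdrawal | 10% | 20% |
|---|---|---|---|
| Above the model's dose | 1.6–9.0% | 4.5–16.1% | 8.7–29.7% |
| Above it and over the 40% ceiling | – | 1.0–8.5% | 2.1–14.3% |
| Two or more levels above latest patient | – | 0.2–1.4% | 0.9–3.1% |
| Below the model's dose | – | 11.8–33.3% | 22.9–58.3% |

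**Effect on the MTD.** A separate run (2,000 per setting, linear weight, run-in counted as the first 6 enrolled) compared same-level with model-dose replacement. The largest gap in selection or stopping shares was 2.0 points at 10% withdrawal (stopping 0.194 v 0.214) and 3.8 at 20% (Level 3 selected 0.300 v 0.262). Monte Carlo SE is up to about 1.5 points.

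**The case against.** The best reply is that the heading of 10.2.3 limits it to non-evaluable patients, and 5.4 makes anyone with one fraction evaluable. Replacement would then apply only to patients who leave untreated. The model would have moved little by then, and the old level would usually match the new one. But the body of 10.2.3 turns on whether a DLT has already occurred, which presupposes treatment, so this reading does not settle the matter.

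A second reply is that a specific rule overrides a general one, making 10.2.3 a deliberate exception. If so, it is an exception that lets a patient be dosed past the design's own safety limits, which is the objection.

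Third, 10.1.2 allows a dose change once cumulative exposure reaches 6 months. If that is counted per level, patient 8's move to Level 3 in the worked history comes too soon. The plan does not say how it is counted. A variant with 6 months of Level 2 exposure first still puts Level 3 at 0.416–0.427 after one more DLT, so this affects the illustration and not the mechanism.

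Some of the case against stands. Treatment is five fractions, patients who stop early are still followed (5.7), and loss to follow-up takes three missed visits and failed contact (5.9), so the 20% withdrawal results deserve little weight. Level skips are rare, and replacements below the model's dose are commoner than those above it. The statistician's update at each enrolment would reveal a mismatch before treatment, but the text would not say how to resolve it.

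**Conclusion.** The concern holds. After the run-in, 10.2.3 and 10.2.1 can require different doses for the same patient, and following either means departing from the other. Departure from the model's dose is the main conflict, a breach of the 40% ceiling is less common, and a breach of the one-level limit is rare. The stake is the dose given to an individual reirradiated patient; the effect on the final MTD is small. The existence of the conflict rests on the text alone. The frequencies rest on assumed withdrawal rates, prior SDs, weight shapes and toxicity curves, and are not the trial's operating characteristics. The frequency and MTD runs also counted the run-in differently (six evaluable v first six enrolled), so they are not strictly comparable. The plan does not say that a withdrawn patient's follow-up is discarded, and no such claim is made here.

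**What to change.** Reword 10.2.3 along these lines:

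> During the run-in, a replacement is treated at Dose Level 1. After the run-in, a replacement is treated as any newly enrolled patient, at the model's current recommended dose under the limits in 10.1.2 and 10.2.1. The withdrawn patient, if at least one fraction was given, stays in the model at the weight for the time observed.

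The last sentence only aligns the section's heading with 5.4. The change removes the conflict by construction and leaves the sample size and every other figure as they are. It costs an amendment of wording. The one downside is that a dose level may end with fewer fully observed patients than same-level replacement would give.
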